## Outcomes

The primary outcomes included the safety profiles, as well as the social deficits as measured by the caregiver-rated Social Responsiveness Scale (SRS) (Gau, 2013), since theoretically targeting the pSTS is aimed to modulate the activity within the social brain network. Atypical social cognition is often associated with the autistic symptoms. The secondary outcomes thus included two common tasks assessing the social cognition performances of people with ASD (Barahona-Correa et al., 2018), i.e., the Reading the Mind in the Eyes test (RMET) (Baron-Cohen, Wheelwright, Hill, Raste, & Plumb, 2001; T. S. Li et al., 2020) and Frith-Happe Animations Task (White, Coniston, Rogers, & Frith, 2011) (Barch et al., 2013). Notably, these two tasks, nonetheless, are not specific to the pSTS activities. Given our preliminary beneficial results in compulsory behaviors in adults (Ni et al., 2017), we also adopted the Repetitive Behavior Scale-Revised (RBS-R) (Bodfish, Symons, Parker, & Lewis, 2000; Y. C. Yang et al., 2019) as the exploratory outcome. Higher scores on the SRS and RBS-R represent greater severity of the two domains of autistic symptoms. RMET total scores represent how many correct mental states the participant has inferred from the eyes, indicating

individual's theory of mind capability. Frith-Happe Animations also tap mentalizing capacity by asking the participant to infer whether interaction intents exist between two triangles. When the participant answered about the presence/absence of interactions, he/she was further asked to select words that best described how these triangles were feeling at the end of each video clip. Participants scored 1 point for correct answers to either presence/absence or exact description of mental states, which are summarized as the total Categorical scores and Feelings scores, respectively. To enhance a contrast and reduce assessment time, we adopted the revised Frith-Happe Animations following those used in the Human Connectome Project (Barch et al., 2013), which only included social and random interactions.

Side effects were assessed immediately after each session and at one-month follow-up using open-ended questions inquiring any physical discomfort and then close-ended questions including "pain at application site", "headache/dizziness", "tinnitus" and "anxiety" experienced during and after iTBS

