Considering clinical heterogeneity in ASD, we defined responders based on the Reliable Change Index (RCI) calculated using the SRS total scores. The RCI takes into consideration the false positive outcome that could occur due to random error from repeated measurements alone (Jacobson & Truax, 1991). The RCI represents differences in individual's scores between before- and after-intervention, divided by the standard error of the difference of the measure. Responders were those with RCI  $>1.64$ , which corresponds to  $p<0.05$  with one-sided test (i.e., the null hypothesis was that iTBS would not help with social symptoms). Demographic and clinical features were compared between the responders and non-responders using non-parametric tests.

In addition to the stratified analysis based on responsiveness, we also tested a three-way interaction (Active vs. Sham  $\times$  Time  $\times$  Modifier) to explore whether iTBS over the pSTS is more beneficial for individuals with ASD with certain characteristics. Effect modifiers included demographics, intelligence quotient, clinical traits, comorbidity, and medication.

Statistical analysis was performed using the SAS Version 9.4 software (SAS Institute, Cary, NC, USA). Considering multiple comparisons including the clinical symptoms and social cognitive function (5 measurements), the GEE, within-group analyses and three-way interaction were considered statistically significant at  $p\text{-value}\leq0.01$ . Despite contention, herein, alpha level in-between 0.01 and 0.05 were considered a nominal significance for hypothesis generating for the future study (Bays, 2019).

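### The flat 0.01 threshold is valid but more conservative than it needs to be: it fits Bonferroni over five scores, one of them exploratory, where Holm over the four primary and secondary scores would give more power under the same 5% family-wise limit

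*Combined protocol and SAP*

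**What the plan says.** The Statistics section justifies its threshold by the number of scores and applies one cut-off, p≤0.01, to three kinds of analysis: "Considering multiple comparisons including the clinical symptoms and social cognitive function (5 measurements), the GEE, within-group analyses and three-way interaction were considered statistically significant". Results above that cut-off are downgraded: "alpha level in-between 0.01 and 0.05 were considered a nominal significance for hypothesis generating". No step-down, hierarchical or gatekeeping procedure is described.

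The Outcomes section gives the scores and their rank:

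- Primary efficacy: "the social deficits as measured by the caregiver-rated Social Responsiveness Scale (SRS".
- Secondary: "The secondary outcomes thus included two common tasks assessing the social cognition performances of people with ASD". These are RMET, with one total score, and the Frith-Happe animations, with two scores: "which are summarized as the total Categorical scores and Feelings scores, respectively".
- RBS-R is adopted "as the exploratory outcome. Higher scores on the SRS and RBS-R represent greater severity of the two domains of autistic symptoms".

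The plan neither lists the five measurements nor writes out the division that leads to 0.01.

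**The concern.** Two features of the rule cost power without buying error control for the primary and secondary outcomes.

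1. Single-step Bonferroni holds every score to the strictest threshold, even after other scores have been rejected. Holm's procedure has the same family-wise guarantee under any correlation between the scores, and on the same family it rejects everything that Bonferroni rejects.
2. Counting RBS-R lets an outcome that the plan ranks as exploratory tighten the bar for the primary and secondary scores from 0.05/4 to 0.05/5.

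At stake is how p-values between 0.01 and 0.05 are labelled. Some that the plan would call merely nominal could be claimed at the same 5% family-wise limit. This affects the secondary tasks most, because the later Holm steps are the generous ones.

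**Working it through.** **Step 1. Reproduce the threshold.** SRS (1) + RMET (1) + Frith-Happe Categorical and Feelings (2) + RBS-R (1) = 5, and 0.05/5 = 0.01, the plan's figure. Without RBS-R the count is 4 and 0.05/4 = 0.0125. That 0.01 is Bonferroni over these five is an inference, but it fits both the stated count and the stated cut-off.

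**Step 2. Holm over the four primary and secondary scores.** Order the p-values and compare the j-th smallest with 0.05/(4 − j + 1), stopping at the first that fails:

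- 0.05/4 = 0.0125
- 0.05/3 = 0.0167
- 0.05/2 = 0.025
- 0.05/1 = 0.05

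All four steps exceed 0.01, so any of these scores that is significant under the present rule stays significant.

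**Step 3. Is 75% power at 0.01 a fair starting point?** The Design section gives a minimum total of 68, 90% power, two-sided 5% and a standardized effect of 0.4 for a within-between interaction. It does not give the number of measurements m, their correlation ρ, or whether 0.4 is d or f. With λ = f²·N·m/(1 − ρ), and assuming two equal arms, f = 0.2 (d = 0.4), m = 2 and ρ = 0.5:

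- λ = 0.04 × 68 × 2 / 0.5 = 10.88, on 1 and 66 df.
- Power at 0.05 is 90.2%, and 68 is the smallest even total that reaches 90%. The plan's figure is reproduced.
- Power at 0.01 is 73.9%; at 0.0125 it is 76.5%.

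Other choices do not return 68. For example, f = 0.2, m = 3, ρ = 0.5 needs 56; at N = 68 those inputs give 86.0% at 0.01 and 87.7% at 0.0125. So 75% is realistic for this trial, but it rests on assumed inputs.

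**Step 4. Gain from Holm over four.** Power of 75% at two-sided 0.01 means a noncentrality of 2.576 + 0.674 = 3.250. The first Holm step alone gives Φ(3.250 − 2.498) = 77.4%. Simulation of four correlated normal statistics (400,000 draws; correlation 0, 0.3, 0.5) gives the power for each score that truly has an effect:

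| Scores with an effect | Flat 0.01 | Holm over four |
|---|---|---|
| 1 | 75% | about 77.5% |
| 2 | 75% | 79.5–80% |
| 3 | 75% | 82–83% |
| 4 | 75% | 85–87% |

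With no effect on any score, family-wise error over the four is 3.5–3.9% at flat 0.01 and 4.3–4.9% under Holm.

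**Step 5. Where the gain comes from.** Take the Step 3 inputs, full effects on all scores and zero correlation. Flat 0.01 gives 73.9%, Bonferroni over four 76.5%, Holm over all five 86.1%, and Holm over four 87.2%. When several scores respond, most of the gain comes from the step-down. When only SRS responds, nearly all of it comes from dropping RBS-R (73.9% to about 76.6%).

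**Step 6. The condition on the 5%.** The guarantee is for one test per score. The plan's GEE fits Treatment, Time and their interaction over Baseline, Week 4 and Week 8, and names no single term or visit as the test. Suppose instead that two visit contrasts per score were tested (assumed correlation 0.3–0.7 within a score and 0–0.3 between scores, no true effects). The chance of at least one false positive over four scores would then be about 6.6–7.7% at 0.01 and 8.2–9.5% at 0.0125. The test has to be named before the threshold is relaxed.

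**The case against.** The strongest objection is that nothing here is wrong: 0.01 over five scores is a valid, cautious rule, and counting an exploratory score that will itself be tested is conservative, not contradictory. This stands. A reader might infer that the plan miscontrols error or contradicts itself; for one test per score the documents support neither.

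Three further objections also stand and narrow the point.

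- **Undefined test.** The 5% guarantee is conditional on naming one between-arm test per score, as Step 6 shows.
- **Timing.** The text reads as written after data were seen. The Statistics section reports a baseline RMET difference, the Intervention section reports that no sham participant disclosed or guessed the allocation, and the Community involvement section says findings were fed back to families. Relaxing a threshold and dropping an outcome at that stage could relabel known results.
- **Size.** A reader might take a gain of ten points or more as the general expectation. That needs effects of full size on all four scores, which the documents do not establish; the Outcomes section itself notes that the two tasks are not specific to pSTS activity. If one score alone responds, the gain is about 2.5 points.

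It can also be said that pooling SRS with the secondary scores is not the most powerful choice for SRS. If SRS were the sole primary efficacy test at 0.05, its power would be Φ(3.250 − 1.960) = 90.1%. That is a legitimate alternative and is included in the fix.

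None of this removes the point: with one named test per score, Holm over the four keeps every rejection that the present rule makes on them, and can add more, within the same 5%.

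**Conclusion.** The point holds as an efficiency improvement. The present threshold is valid but needlessly strict for the four primary and secondary scores. Holm over those four raises power per truly affected score from an assumed 75% to about 77.5% (one score affected) and up to 85–87% (all four), with family-wise error at or below 5%.

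This rests on four assumptions: 0.01 is 0.05/5 with RBS-R among the five; there is one between-arm test per score; power at 0.01 is near 75%; and the correlation between scores is 0 to 0.5. The domination of the present rule on the four scores does not depend on the last two.

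A reader might infer that the change recovers the planned 90% power. It does not: with the Step 3 inputs, Holm over four reaches at most 87.2% in the scenarios tried. Nor does it touch the within-group and three-way interaction tests, whose error neither rule controls.

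**What to change.** 1. Name one between-arm test per score, for example the Treatment × Time term of the GEE.
2. Apply Holm to SRS, RMET, Frith-Happe Categorical and Frith-Happe Feelings: ordered p-values against 0.0125, 0.0167, 0.025 and 0.05, stopping at the first non-rejection.
3. Report RBS-R with estimate and confidence interval outside the family.
4. Keep the within-group and three-way interaction tests at 0.01 and label them exploratory.
5. Alternatively, declare SRS the sole primary efficacy test at 0.05 and apply Holm to the three secondary scores. The 5% then holds within each tier; for a 5% statement over all four scores, test the secondaries only if SRS is significant.
6. If outcome data have already been seen, keep 0.01 as the planned rule and report Holm as a labelled post hoc sensitivity analysis.

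**Cost.** A few sentences of SAP wording, with no new data or participants. RBS-R loses its error-controlled claim, which agrees with its exploratory label. Holm has no simple matching simultaneous confidence intervals; the plan uses none.

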### Statistics

Herein we only reported clinical and cognitive data during RCT. Independent t-test and chi-square test were used to evaluate the difference of baseline characteristics. To simultaneously examine the immediate effect of pSTS vs. sham stimulation in different visits, the generalized estimating equations (GEE) model was conducted using the data of Baseline, Week 4, and Week 8. To account for correlations between individuals' repeated measurements between visits, a working correlation matrix with a first-order autocorrelation was used with the robust estimator of standard error. Treatment, Time, and a two-way interaction (Active vs. Sham  $\times$  Time) effects were modeled in the GEE. The maximum likelihood method in the GEE was used to address the missing values from dropouts. In consideration of high inter-individual variability in the clinical symptoms and social cognitive function at baseline, we also implemented an additional analysis using the symmetrized percentage change (Ayers, 2006) to investigate the iTBS effects. Because there was significant difference for both groups at baseline in the RMET, all of the analyses in the GEE and symmetrized percentage change were adjusted.

To comprehensively examine effects across time for both conditions, exploratory within-group comparisons were also conducted in the same GEE regardless of whether the main effect was statistically significant. However, when the main effect of GEE is not statistically significant, the significant findings in these exploratory within-group comparisons should be interpreted conservatively. The correction for multiple comparisons was implemented to avoid type-I errors. Five pairwise within-group comparisons (i.e., Baseline vs. Week 4, Baseline vs. Week 8, Baseline vs. Week 12,

Week 4 vs. Week 8, Week 8 vs. Week 12) were calculated separately in Active (8-week active TBS) and Sham (4-week sham followed by 4-week active TBS) groups.

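### The 0.01 threshold corrects for the five outcome measures only, yet it also declares significance for 50 within-group contrasts and an unlisted set of three-way interactions

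*Combined protocol and SAP*

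**What the plan says.** All of this is in the Statistics section, with the outcome scores defined under Outcomes.

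- **Basis of the threshold.** "Considering multiple comparisons including the clinical symptoms and social cognitive function (5 measurements"). The plan does not list the five. They are evidently the SRS, the RBS-R, the RMET and two Frith-Happe scores, "which are summarized as the total Categorical scores and Feelings scores, respectively".
- **Scope of the threshold.** "the GEE, within-group analyses and three-way interaction were considered statistically significant at" p ≤ 0.01. Results between 0.01 and 0.05 are treated as nominal and hypothesis-generating.
- **Within-group tests.** "Five pairwise within-group comparisons (i.e., Baseline vs. Week 4, Baseline vs. Week 8, Baseline vs. Week 12", then Week 4 vs. Week 8 and Week 8 vs. Week 12; these "were calculated separately in Active (8-week active TBS) and Sham (4-week sham followed by 4-week active TBS) groups".
- **Their status.** The "exploratory within-group comparisons were also conducted in the same GEE regardless of whether the main effect was statistically significant". The plan asks for cautious reading if the main effect is not significant.
- **Claim of control.** In the same paragraph, just before the contrasts are listed: "The correction for multiple comparisons was implemented to avoid type-I errors".
- **Three-way interactions.** "Effect modifiers included demographics, intelligence quotient, clinical traits, comorbidity, and medication". Their stated purpose is to explore. The variables in each category are not given.

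**The concern.** The divisor of five accounts for the number of outcomes and for nothing else. Within each outcome there are ten within-group contrasts and several modifier tests, all judged at the same 0.01. The plan describes no further adjustment for contrasts, arms or modifiers.

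What is at stake is the meaning of the label. Because the plan keeps the hypothesis-generating description for p between 0.01 and 0.05, a within-group change or a modifier effect at p = 0.008 is reported in the same terms as the randomised comparison. A reader who sees the sentence on correction will take such a result as protected against multiplicity, which it is not. The advice on cautious reading does not close the gap: it covers only within-group comparisons, and it lapses when the main effect is significant. No such advice covers the modifier tests.

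**Working it through.** **Inputs from the plan.** Overall level 0.05 (two-sided 5% in Design; also the upper end of the nominal zone in Statistics). Five measurements. Five contrasts per arm, two arms. Five modifier categories. Per-test cut-off 0.01.

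**1. Reproduce the threshold.** 0.05 / 5 = 0.01, an exact match. The whole 5% is spent on one test per outcome.

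**2. Count the tests.**
- Between-arm: one interaction test × 5 outcomes = 5.
- Within-group: 5 contrasts × 2 arms × 5 outcomes = 50. This follows directly from the text.
- Three-way: 5 categories × 5 outcomes = 25. This assumes one variable per category and all five outcomes. Some categories are worded in the plural, so 25 is a plausible minimum, but the plan does not state it.

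**3. Family-wise error if all nulls are true.** For k independent tests it is 1 − 0.99^k. The bound under any dependence is k × 0.01.

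| Family | k | Independent | Bound |
|---|---|---|---|
| Between-arm | 5 | 4.9% | 5% |
| Within-group, one outcome | 10 | 9.6% | 10% |
| Within-group, all outcomes | 50 | 39.5% | 50% |
| Three-way (assumed count) | 25 | 22.2% | 25% |
| Within-group and three-way together | 75 | 52.9% | 75% |

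**4. Allow for correlation.** The contrasts share visits and the outcomes are related, so independence overstates the within-group figure. The five contrasts were simulated over four visits with normal test statistics, two independent arms and 200,000 runs per setting. The plan gives no correlations; those used are assumptions: first-order autoregressive between visits (0.5 or 0.8) and equal between outcomes (0 to 0.9).

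| Outcome correlation | Visit correlation 0.5 | Visit correlation 0.8 |
|---|---|---|
| 0 | 34.8% | 34.1% |
| 0.3 | 33.1% | 32.3% |
| 0.6 | 27.9% | 27.2% |
| 0.9 | 17.6% | 17.2% |

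For one outcome alone, the five contrasts in one arm give 4.25% (visit correlation 0.5) or 4.06% (0.8). Over two arms: 1 − (1 − 0.0425)² = 8.3%, or 1 − (1 − 0.0406)² = 8.0%. With the independent value of 9.6%, the range is about 8–10%.

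**5. Level needed for the full family.** Bonferroni over 50 tests is 0.05/50 = 0.001; over 25 tests it is 0.05/25 = 0.002.

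**The case against.** The strongest reply is that these tests are exploratory and that the plan says so. It names the five measurements openly, so a careful reader can see that the correction is per outcome. The sentence on type-I errors states a purpose and makes no explicit promise of family-wise control over 50 tests. The cautious-reading rule covers the most misleading case, a null between-arm result beside significant within-arm changes. Full family-wise control of exploratory contrasts is a matter of judgement. All this stands as a reason for lower severity. It does not remove the fault, because the plan still attaches the significance label at 0.01 to these tests.

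The error rates assume that all nulls are true. Both arms include active stimulation at some point, and repeated ratings can drift without any treatment effect, so some within-group nulls may well be false. More basically, within-group contrasts do not compare treatments, and no multiplicity adjustment cures that. This also stands, and it favours dropping the label over adjusting it.

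Some stronger readings are tempting but not supported:

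- *A false significant finding is likely.* Neither family passes one half. Only the two pooled under independence do (52.9%), and that uses the assumed 25.
- *The plan promises 1% error across the contrasts of one outcome.* It gives 0.01 as a per-test cut-off and says nothing about a per-outcome rate.
- *There are at least 25 interactions.* The plan gives categories without variables, so this is an inference.
- *The between-arm result is compromised.* With one interaction test per outcome it stays within 5%.

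**Conclusion.** The point holds, at moderate weight. The only correction described is for five outcomes, and it does not deliver type-I error control for the within-group contrasts, where the plan's statement about correction sits. The excess above 5% appears under every correlation tried, so the conclusion does not depend on a particular choice; the exact size does. The simulation approximates the planned GEE and does not refit it. The three-way figure is weaker evidence than the within-group one, since it rests on an assumed count and on independence. What changes is which secondary statements the trial may call statistically significant; the randomised comparison per outcome is untouched.

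**What to change.** Keep p ≤ 0.01 as the significance rule for the between-arm Group × Time test of each outcome, and state that 0.01 corrects for outcomes only. Report within-group and three-way results as exploratory estimates with confidence intervals, without the significance label. List the modifier variables that were tested.

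If the label is to be kept, name each family and apply Holm at 0.01 within each outcome:

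- across its 10 within-group contrasts, with the smallest p compared with 0.01/10 = 0.001;
- across its modifiers, in the same way.

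Each family is then bounded at 5 × 0.01 = 5% under any correlation. This control is separate for each: the between-arm, within-group and three-way families together could still reach 3 × 5% = 15%, and the text should say so.

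The cost is wording and reporting; no new data are needed and the main comparison is unchanged. The downside is that fewer exploratory results will be called significant. The document is written in the past tense and mentions an observed baseline difference, so an added Holm step would be retrospective and should be disclosed as such. Removing the label is the simpler course.

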### **Community involvement**

There were no community stakeholders involved in the development of research questions, study design and outcome measurements. Taipei Parents Association of Autism and Foundation for Autistic Children and Adults in Taiwan helped us to disseminate the recruitment notice during the study implementation, as well as provided the platform for knowledge translation and dissemination of the current findings to parent groups after the completion of the study. The progress report has been submitted to the funding agency, and the findings have been summarized in a user-friendly language and been feedbacked to the participants and their caregivers.

